7.0 STATISTICAL CONSIDERATIONS

7.1 Primary Objective

The primary objective is to estimate the incidence of treatment-related major financial hardship (debt, selling/refinancing home, borrowing money from friends/family, ≥ 20% income decline) among evaluable patients with newly diagnosed metastatic colorectal cancer (mCRC) treated at NCORP sites.

Given serial measurements, the primary endpoint is time to first evidence of major financial hardship. Dropout due to death from mCRC will be a significant factor in this study. Recent randomized clinical trial data have reported 1-year survival of around 60% for this population. (19) Therefore death represents a substantial competing risk in the detection of financial hardship, which is accounted for in the study design. Both time to first evidence of major financial hardship and death are assumed to exhibit exponential decline. Dropout for reasons other than death (e.g. transferring care to another institution, withdrawal of consent) following enrollment in the study is estimated to be around 10% based on other studies in the literature. (20,21) Non-death related dropouts will be censored.

Based on preliminary data, we anticipate that 40% of patients will experience major financial hardship at some point in the first year after diagnosis. Estimates of major financial hardship at 1 year will be derived using cumulative incidence to account for competing risks.

Under this scenario, a sample size of n=320 eligible, evaluable patients will allow us to estimate the confidence interval to within \pm 8% (based on the upper bound of the 95% confidence interval using an exact binomial in patients with complete follow-up), if the assumed incidence is at least 40%. Thus this sample size will allow us to estimate the confidence interval to within \pm 20% of the assumed incidence (the "relative accuracy"). The relative accuracy will improve with higher incidence as shown in the table below. This estimate is conservative as it is based on the assumption of no information from the 50% of patients estimated to drop out.

| Assumed incidence (p) | 95% confidence interval about p | Confidence range | Relative accuracy [(95% CI upper bound – p)/p] |
|-----------------------|---------------------------------|------------------|--|
| 20% | 14.1% - 27.0% | ± 7.0% | ± 35.2% |
| 30% | 23.0% - 37.7% | ± 7.7% | ± 25.8% |
| 40% | 32.3% - 48.0% | ± 8.0% | ± 20.1% |
| 50% | 42.0% - 58.0% | ± 8.0% | ± 16.0% |

Given non-restrictive eligibility criteria, we anticipate a low rate of ineligibility (5%). In addition, 10% of patients are anticipated not to complete their baseline forms and will be inevaluable. Therefore 374 total patients will be enrolled to obtain 320 eligible, evaluable patients.

The total number of patients experiencing at least one financial hardship at each study interval will be determined. The proportion of patients experiencing multiple financial hardships will also be reported.

7.2 Secondary Objectives

Risk Factors for Financial Hardship

Sample size calculation will be driven by the key secondary objective of this study, which is to assess whether major financial hardship at one year differs by age (< 65 vs. \geq 65), race (white vs. non-white), marital status (married vs. unmarried), employment status (any employment vs. unemployed), and income (household income < \$50,000 / year vs. \geq \$50,000 / year). In particular, we hypothesize that financial hardships are more likely in patients who, at diagnosis, are younger, non-white, unmarried, unemployed, or have lower incomes.

With a series of 5 hypotheses to be tested, we account for multiple comparisons using a conservative Bonferroni alpha = 0.01 two-sided test for each comparison. Three years of accrual with one year of follow-up is anticipated. Based on a two-sample survival design accounting for the competing risk of death (40% deaths at 1 year [hazard rate of 0.51]), n=320 eligible, evaluable patients will give 90% power to detect an absolute difference of 20% (that is, 30% rate at year 1 in good performing group [hazard rate 0.356] vs. 50% in poor performing group [hazard rate of 0.693]) in the proportion of patients with major financial hardship, if a ratio of patients between two groups is 1:1. This corresponds to a hazard ratio of 1.95. Power drops to 83% if the ratio of patients in subgroups is 2:1.

The effect of age, race, marital status, employment status, and income on major financial hardship will be estimated using multivariable Cox regression. The regression will include the 5 covariates of interest plus insurance status, education, and gender. A sample size of 320 eligible patients ensures that the ratio of events to independent predictors will be at least 10:1. (22, 23)

Major Financial Hardship and HRQOL:

A secondary objective of this study is to assess the relationship between major financial hardship and HRQOL. These factors are likely positively correlated and associated with the same general status of poor prognosis (endogenous factors). analysis that evaluates, from baseline, the association of major financial hardship and HRQOL will find a positive correlation as an artifact of the endogeneity, and adjustment for performance status is unlikely to fully account for this. Therefore we will use landmark analysis to establish major financial hardship as a baseline predictor of HRQOL. In particular, patients will be categorized as having major financial hardship at their 3 month assessment (yes vs. no). We will then use linear regression to assess whether the 3month assessment of financial hardship predicts the 6-month HRQOL score. HRQOL at 3 months will be included as an adjustment covariate. The 6-month HRQOL score will be based on the EORTC QLQ-C30 questionnaire transformed into a linear score (0 to 100) using the EORTC scoring manual. A difference in mean score of ≥ 10 between time points is considered clinically relevant. In addition, to assess the robustness of potential associations between major financial hardship and HRQOL to large changes in a subset of patients, HRQOL at 6 months will also be categorized as decline vs. no decline and logistic regression performed. This analysis is limited by the fact that patients without 6 months follow-up scores are more likely to be worse prognosis patients that may also be related to predictive factors of interest (that is, age, race, marital status, employment status, and income).

Feasibility

The feasibility of successfully accruing to a prospective-multi-site longitudinal cohort study assessing financial outcomes in patients with metastatic colorectal cancer (mCRC) undergoing treatment within the NCORP network will be examined. The total anticipated accrual time is 3 years. To be conducted in that timeframe, each of the NCORP components (we anticipate 25 NCORP components) will each need to enroll, on average, about 5 patients per year. Accrual will be monitored regularly. Given the open eligibility criteria, we hypothesize that enrollment will be feasible. However accrual will be assessed at 1.5 years after study activation. If monthly average accrual in quarters 5-6 after study registration is < 50% of projected accrual, efforts will be made to increase accrual over the succeeding 6 month period. If after 2 years, monthly accrual remains < 50% of projected accrual, study revision will be considered. In order to address the potential for selection bias, we will compare demographics (age, race, gender, etc.) of the final cohort to the typical patient population seen at the various practice sites.

The feasibility of incorporating a caregiver component to the study will also be examined. Caregiver participation is optional. The caregiver component will be considered feasible if the designated caregivers for > 50% of eligible patients complete and submit their baseline and at least one follow-up assessment. We will use means, medians, proportions to describe the participating caregiver population. Our analyses will be largely descriptive. We will look at the proportion of caregivers who experienced changes in employment and expenses (caregiver questionnaire items 11 and 13). We expect that caregivers of patients who experience financial hardship will be more likely to report financial burden. We will therefore investigate the association between patient-reported financial hardship and level of caregiver-reported financial burden. We will compare proportion of caregivers experiencing 'high financial burden' (≥ 3 on Likert scale) for patients who do vs. do not report major financial hardship using two-sample t tests. If our caregiver accrual is very poor (<20%), we will focus on describing the patient population rather than attempting to correlate caregiver and patient responses.

7.3 Other Secondary Endpoints:

The linkage of clinical and financial data with credit histories obtained from TransUnion will allow us to explore additional indicators of financial stress, including high balances

and past due amounts of credit card and bankcards as well as evidence of bankruptcies, liens, and collections or repossessions. These data will also allow us to corroborate self-reports of debt and bankruptcy in order to investigate the reliability of self-reports in estimating financial hardship. Credit reports will be obtained at baseline and at 6 and 12 months after registration. Given the poor 1-year survival for this patient cohort (60%), multiple post-baseline credit reports are requested to limit bias due to missing data related to death.

Other secondary objectives including measurement of out-of-pocket expenses, health insurance changes, changes in assets/income/wealth, measurement of debt and spending by credit report histories, and assessment of patient, caregiver, and bereaved caregiver financial stress will be handled using descriptive statistics (e.g. mean, median, proportions). We will use descriptive statistics to summarize baseline patient characteristics and will compare populations using two-sample means and proportions tests (α level 0.05). Caregiver strain index will be scored based on responses (score range 0 to 26). Mean scores will be compared for caregivers of patients reporting vs. not reporting at least one financial hardship.

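### Testing the five risk factors at a fixed Bonferroni 0.01 is valid, but Holm's step-down procedure would give more power at the same 5% family-wise error, with the gain depending on how many factors are real

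*Combined protocol and SAP*

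**What the plan says.** Section 7.2 (Risk Factors for Financial Hardship) lets the sample size be driven by whether major financial hardship at one year differs by age, race, marital status, employment status and income. It hypothesises a direction for all five. The multiplicity rule is: "With a series of 5 hypotheses to be tested", "we account for multiple comparisons using a conservative Bonferroni alpha = 0.01 two-sided test for each comparison".

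Power is quoted at that level: "n=320 eligible, evaluable patients will give 90% power to detect an absolute difference of 20" percentage points with equal groups (30% against 50% at one year). "This corresponds to a hazard ratio of 1.95". For unequal groups, "Power drops to 83% if the ratio of patients in subgroups is 2:1".

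The effects are then estimated in one multivariable Cox model holding the five factors plus insurance status, education and gender. No step-down rule is mentioned, no significance level is attached to the Cox model, and no simultaneous confidence intervals are planned.

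**The concern.** A single-step Bonferroni rule holds every test at 0.01 whatever the other four show. Holm's procedure relaxes the threshold for the remaining hypotheses after each rejection and still protects the family at 5%. If several factors are real, the fixed rule therefore leaves some of them undeclared that a rule with the same error guarantee would declare. Only factors with a p-value between 0.01 and 0.05 are affected, but these are the conclusions of the objective that sizes the study. Section 7.2 expects all five factors to matter, which is the situation in which the two rules differ most.

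**Working it through.** **Inputs from Section 7.2.** Five hypotheses; two-sided 0.01 each; n = 320; hardship hazards 0.356 and 0.693 per year; death hazard 0.51; three years of accrual plus one of follow-up; stated power 90% (1:1) and 83% (2:1). Section 7.1 adds about 10% dropout for reasons other than death, a hazard of −ln(0.9) = 0.105.

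**1. The plan's own figures.** 0.05/5 = 0.01. Hazard ratio 0.693/0.356 = 1.947. With uniform accrual over three years and follow-up to study end, the chance of an observed hardship event in a group with hazard λ and death hazard μ, where a = λ + μ, is

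P = (λ/a) × [1 − (e^(−a) − e^(−4a))/(3a)].

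This gives 0.350 and 0.529, so with 160 per group the expected events are 160 × (0.350 + 0.529) ≈ 141. Schoenfeld's formula, with w the fraction of patients in one group, is

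power = Φ(√(events × w(1 − w)) × ln HR − 2.576).

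- 1:1: Φ(√(140.6/4) × 0.666 − 2.576) = Φ(1.37) = 91.5%, or 89.0% with dropout. Stated: 90%.
- 2:1 (larger group at lower risk): 131 events, 84.6%, or 81.1% with dropout. Stated: 83%.

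Both stated figures are reproduced to within 2 points.

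**2. Why Holm is safe and never worse.** Holm orders the five p-values and compares them with 0.05/5, 0.05/4, 0.05/3, 0.05/2 and 0.05/1, that is 0.01, 0.0125, 0.0167, 0.025 and 0.05, stopping at the first failure.

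- No threshold is below 0.01, so every p-value that passes Bonferroni passes Holm.
- With m true nulls, the first true null to be rejected must meet a threshold no larger than 0.05/m. The chance that any of the m does so is at most m × 0.05/m = 0.05, whatever the correlation.

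**3. Size of the gain.** Five two-sided z-tests were simulated. Each true factor has mean z(0.995) + z(power): for 90%, 2.576 + 1.282 = 3.857. The documents give no correlation between the tests. Zero is the base assumption, with 0.3 and 0.6 as the range.

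| Real factors (of 5) | Power per true factor at the 90% design point: Bonferroni → Holm | Same at 83% (2:1) |
|---|---|---|
| 1 | 90% → 90% | 83% → 83% |
| 2 | 90% → 91.2% | 83% → 84.7% |
| 3 | 90% → 92.6% | 83% → 86.6% |
| 4 | 90% → 94.3% | 83% → 89.1% |
| 5 | 90% → 96.6% | 83% → 92.5% |

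With all five real and correlation 0.3, the 90% becomes 95.9%; with correlation 0.6 it becomes 95.0%. The chance of declaring all five, independent tests, goes from 0.9^5 = 59% to 86% at the 90% design point, and from 0.83^5 = 39% to 73% at 83%.

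Holm's simulated family-wise error was at most 4.9% in every scenario, and no run had a Bonferroni rejection that Holm missed.

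**The case against.** **Bonferroni is valid, pre-specified and openly called conservative.** This stands. Nothing in Section 7.2 is contradictory or inflates error. The primary objective, an estimate of incidence, is untouched, and so are n = 320 and the 0.01 used to size the study.

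**The gain depends on how many factors are real.** This also stands. A reader might take the five-factor figures as the expected gain. Section 7.2 does hypothesise all five, but the preliminary study in Section 2.0 names only younger age and lower income as most closely associated with hardship. With two real factors the gain at the design point is 1.2 points; with one it is nil. Nor does the plan set detection of all five as a goal, so the rise from 59% to 86% should not be the headline.

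**Single-step Bonferroni buys something.** A reader might infer that the power is given up for no return. That goes too far: a test at 0.01 agrees exactly with a 99% interval, and Holm has no equally simple matching intervals. The documents do not plan such intervals, so the loss is small.

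**Uneven groups.** A reader might infer that Holm cures weak power for race. The accrual table in Section 2.0 expects 74 non-white patients of 374, about 4:1, and the plan quotes no power for that split. Per-test powers such as 78%, 68% and 46% (1:1, 2:1 and 4:1) are not in the documents. They arise if follow-up is assumed to stop at 12 months for each patient, which is a separate question. Taking 46% for race as an assumption, Holm gives 46% if race alone is real, about 52% if two other factors at 78% are also real, and about 62% if all five are. The imbalance remains the main problem.

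**Conclusion.** The point holds as an efficiency improvement to a key secondary analysis, and the plan contains no error here. Holm keeps family-wise error at or below 5% and adds 0 to 6.6 points of power per true factor at the 90% design point, rising with the number of real factors. With all five real at the plan's 83%, the gain is about 9.5 points (83% to 92.5%). That Holm controls error and never rejects less rests on no modelling assumption. The sizes do: they use normal test statistics as an approximation to the Cox tests, equal power for every true factor, and independent tests (slightly smaller gains if positively correlated).

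**What to change.** Replace the Bonferroni sentence in Section 7.2 with: *The five hypotheses, tested by the p-values for the five covariates in the multivariable Cox model, will be tested by the Holm step-down procedure at family-wise two-sided alpha 0.05.* This also settles which p-values form the family.

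Keep alpha = 0.01 in the sample-size calculation. It is Holm's first step, so any power quoted at 0.01 is a lower bound for Holm and n = 320 need not change.

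If 99% intervals for the five hazard ratios are shown, add a note that a factor declared significant at a later Holm step may have an interval that includes 1.

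The cost is one sentence and that note, with no extra patients or data. The change must be made before the results are seen.

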| Racial Categories | Not Hispanic or Latino | | Hispanic or Latino | | |
| | Female | Male | Female | Male | Total |
| American Indian/Alaska Native | 1 | 1 | 0 | 0 | 2 |
| Asian | 13 | 15 | 0 | 0 | 28 |
| Native Hawaiian or Other Pacific Islander | 1 | 1 | 0 | 0 | 2 |
| Black or African American | 20 | 22 | 0 | 0 | 42 |
| White | 123 | 141 | 17 | 19 | 300 |
| More Than One Race | 0 | 0 | 0 | 0 | 0 |
| Total | 158 | 180 | 17 | 19 | 374 |

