4.7 Criteria for Removal of Patient from Protocol Participation

- a. Patient completes 12 months of study participation.
- b. Patient does not receive at least one cycle of chemotherapy within the first 90 days after registration.
- c. The patient may withdraw from the study at any time for any reason. (Research staff should only submit the S1417CD Off Protocol Notice if the patient refuses both direct and indirect follow-up on the study. If the patient allows for indirect follow-up or is refusing to complete any further patient forms but will allow the site to follow them directly, do not submit the S1417CD Off Protocol Notice and continue to submit the site-completed forms at the time points required in Section 9.4b.)
- d. Patient death.

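### The 90% and 83% power stated for the five risk-factor comparisons does not follow from the printed hazards with 12 months' follow-up; it is about 78% at 1:1 and 68–74% at 2:1

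*Combined protocol and SAP*

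**What the plan says.** Section 7.2 (Risk Factors for Financial Hardship) says that the sample size is driven by five two-group comparisons: age, race, marital status, employment and income. Each uses a "conservative Bonferroni alpha = 0.01 two-sided test for each comparison". The power statement is "n=320 eligible, evaluable patients will give 90% power to detect an absolute difference of 20" percentage points at 1:1 allocation, followed by "Power drops to 83% if the ratio of patients in subgroups is 2:1".

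The effect is given as "30% rate at year 1 in good performing group [hazard rate 0.356] vs. 50% in poor performing group [hazard rate of 0.693", with a hazard ratio of 1.95 and a competing death hazard of 0.51 (40% dead at one year). On timing, the section says "Three years of accrual with one year of follow-up is anticipated".

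Other sections limit what is observed:

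- Section 4.7a removes a patient from the protocol when "Patient completes 12 months of study participation". Section 4.9 requires no follow-up after that.
- Section 6.1 confines the endpoint to the 12-month study period.
- Section 7.1 says "Estimates of major financial hardship at 1 year will be derived using cumulative incidence to account for competing risks". It also assumes exponential times for hardship and death, and about 10% dropout for other reasons.
- The accrual table in Section 2.0 has the row "White | 123 | 141 | 17 | 19 | 300" out of a total of 374.

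**The concern.** Three years of accrual plus one year of follow-up, in a conventional survival design with a common closing date, gives each patient between one and four years of observation. This study stops each patient at 12 months, so events in years two to four would be counted in the power but never collected.

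The effect size raises a second question. The printed hazards are the ones that give 30% and 50% when nobody dies, yet the text presents the 20-point gap as a difference in the proportion of patients with hardship, in a design that allows for deaths.

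At stake is the plan's own justification for 320 patients. If true power is well below 90%, non-significant results for age, race, marital status, employment or income would be over-read as evidence of no difference. Race is the most exposed, because its planned split is more unbalanced than any ratio for which power is given.

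**Working it through.** **Inputs.** From Section 7.2: hardship hazards 0.356 and 0.693 per year, death hazard 0.51, n = 320, two-sided alpha 0.01 (z = 2.576). From Sections 4.7 and 4.9: 12 months per patient. From Section 7.1: exponential times and 10% dropout (hazard −ln 0.90 = 0.105). The hazard ratio is 0.693/0.356 = 1.947, and its logarithm is 0.666.

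**Formulas.** The probability that a hardship event is observed is P(h) = h/(h + 0.51) × [1 − mean of exp(−(h + 0.51)t)], averaged over the follow-up times t. With e1 and e2 expected events in the two groups, D = e1 + e2, and f the fraction of patients in one group:

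- Log-hazard test: power = Φ(0.666/√(1/e1 + 1/e2) − 2.576)
- Schoenfeld: power = Φ(0.666 × √(D f(1 − f)) − 2.576)

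**Step 1: reproduce the printed power.** Take uniform accrual over three years and a common close one year later, so t is uniform on 1 to 4 years. Then P = 0.3495 and 0.5294.

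- 1:1: 55.9 + 84.7 = 140.6 events. Log-hazard power = Φ(0.666/√(1/55.9 + 1/84.7) − 2.576) = 90.1%.
- 2:1 with the high-hardship group larger: 37.3 + 112.9 = 150.2 events, power 82.9%.

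Both printed figures are recovered. Schoenfeld gives 91.5% at 1:1 and 84.6–89.8% at 2:1. A simulated log-rank test gives 90.7% and 85.6–87.6%.

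**Step 2: stop every patient at 12 months.**

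- P(0.356) = 0.356/0.866 × (1 − e^−0.866) = 0.2382
- P(0.693) = 0.693/1.203 × (1 − e^−1.203) = 0.4031
- At 1:1: 160 × (0.2382 + 0.4031) = 102.6 events. Schoenfeld power = Φ(0.666 × √(102.6/4) − 2.576) = 78.7%.

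| Allocation, 12 months | Events | Schoenfeld | Log-hazard | Simulated log-rank | Simulated, with 10% dropout |
|---|---|---|---|---|---|
| 1:1 | 103 | 78.7% | 75.3% | 77.6% | 75.4% |
| 2:1, low-hardship group larger | 94 | 67.9% | 73.8% | 74.2% | 72.2% |
| 2:1, high-hardship group larger | 111 | 77.0% | 64.6% | 68.6% | 65.2% |

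The simulations used 20,000 runs. If hardship is detected only at the three-monthly visits, simulated 1:1 power falls further, to about 74%.

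**Step 3: what 90% would need at 12 months.** Schoenfeld requires about 135 events. The mean event probability is (0.2382 + 0.4031)/2 = 0.3207, so about 420 evaluable patients (about 448 by the log-hazard formula). With n = 320 at 1:1, the hazard ratio detectable with 90% power is 2.11, or 2.14 with dropout.

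**Step 4: the effect size.** −ln(0.70) = 0.357 and −ln(0.50) = 0.693, so 30% and 50% hold only if there are no deaths. With the plan's death hazard, the one-year proportions are those in step 2: 40.3% − 23.8% = 16.5 points.

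**Step 5: the other reading.** For cumulative incidences of 30% and 50% with deaths competing, the hazards must be 0.471 and 0.951, a hazard ratio of 2.02. At 12 months and 1:1, events are 160 × (0.30 + 0.50) = 128. Schoenfeld power is 92% at 1:1 and 85–91% at 2:1. With dropout and the smaller group at higher risk, it is 91% at 1:1 and 83% at 2:1.

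**Step 6: race.** 300/374 = 80.2%, so 320 evaluable patients split about 257 to 63. With the printed hazards and the smaller, non-white group at higher risk (the plan's hypothesis), events are 257 × 0.2382 + 63 × 0.4031 = 61.2 + 25.4 = 86.6. Power is about 46% (Schoenfeld) or 60% (log-hazard and simulated). On the step 5 reading, events are 257 × 0.30 + 63 × 0.50 = 108.6, and power is about 63% (Schoenfeld) or 77% (log-hazard).

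**The case against.** The strongest counter-argument is step 5. The text describes a 20-point difference in the proportion with hardship at year one; Section 7.1 estimates hardship by cumulative incidence and anticipates 40% overall, the midpoint of 30% and 50%. On that reading, 12 months of follow-up does give roughly the stated power, and only the bracketed hazards and the hazard ratio need correcting. This stands as far as it goes: the shortfall is conditional on the printed hazards. It does not rescue the paragraph, because it contradicts both printed hazards and the printed hazard ratio, which agree with each other as no-death quantities.

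Other points have partial force:

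- The 1-to-4-year explanation is inferred from the numbers. The plan names no software and no such follow-up pattern.
- At unequal allocation the approximations disagree by up to about 15 points, so the 2:1 and race figures depend on the method.
- All these powers are for unadjusted two-group tests, whereas the plan estimates the effects by multivariable Cox regression.
- The plan makes no power claim at 80:20, so the race figure is an omission and not an arithmetic error.
- The objective is secondary, and the precision calculation for the primary objective is unaffected.

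None of these brings the printed hazards, 12 months of follow-up and 90% power into agreement.

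**Conclusion.** The concern holds. With the printed hazards, death competing and each patient followed for 12 months, power is 75–79% at 1:1 (about 78% simulated) against the stated 90%, and 68–74% simulated at 2:1 (65–77% across the two formulas) against the stated 83%. The type II error at 1:1 is about 22%, roughly twice the stated 10%. The result rests on the plan's exponential assumption and 320 evaluable patients; allowing for the plan's 10% dropout lowers simulated 1:1 power to about 75%.

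If the sponsor meant 30% and 50% as cumulative incidences, the power is about right, but the hazards and the hazard ratio of 1.95 are wrong. On either reading the paragraph is not internally consistent with the 12-month design.

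**What to change.** Recompute the Section 7.2 power with administrative censoring at 12 months and the 10% dropout from Section 7.1, and print one consistent set:

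- **(a) If the printed hazards are intended:** keep 0.356, 0.693 and hazard ratio 1.95; describe the effect as about 24% against 40% cumulative incidence; state power of about 75–79% at 1:1 and about 65–74% at 2:1, or a detectable hazard ratio of about 2.1 for 90% power.
- **(b) If 30% and 50% are cumulative incidences:** print hazards of about 0.47 and 0.95 and hazard ratio 2.02, with the 12-month power that follows.

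In both cases, name the power method, say which group is larger at 2:1, add power for race at the planned 80:20 split, and state that each patient contributes at most 12 months.

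The cost is rewriting one paragraph, with no added patients or procedures. Under (a) the stated power becomes less favourable; keeping 90% at hazard ratio 1.95 would instead take about 420 to 448 evaluable patients before dropout.

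### Section 7.2's 30% vs 50% contrast and its printed hazards cannot both hold once its own death hazard is applied; with those hazards and 12 months of follow-up, power is about 75-79%, not 90%.

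*Combined protocol and SAP*

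**What the plan says.** Section 7.2 (Risk Factors for Financial Hardship) says that this key secondary objective drives the sample size. It describes a two-sample survival design "accounting for the competing risk of death (40% deaths at 1 year [hazard rate of 0.51"]), with 320 eligible, evaluable patients and alpha 0.01 two-sided for each of five comparisons. The detectable effect is a 20-point absolute difference, "30% rate at year 1 in good performing group [hazard rate 0.356] vs. 50% in poor performing group [hazard rate of 0.693"]. This is described as a difference "in the proportion of patients with major financial hardship, if a ratio of patients between two groups is 1:1". The hazard ratio is given as 1.95 and the power as 90%, falling to 83% at 2:1. On timing, 7.2 says: "Three years of accrual with one year of follow-up is anticipated".

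Section 7.1 sets the distributions: "Both time to first evidence of major financial hardship and death are assumed to exhibit exponential decline". It also names the scale for one-year rates: "Estimates of major financial hardship at 1 year will be derived using cumulative incidence to account for competing risks".

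Section 4.7a lists, as a reason for leaving the protocol, "Patient completes 12 months of study participation". Section 4.9 requires nothing after that point, and the calendar in section 5.0 ends at Month 12.

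**The concern.** The bracketed hazards convert 30% and 50% to exponential rates as if hardship were the only event that could occur. The same sentence, however, brings in a death hazard that removes 40% of patients in the first year. A patient who dies first can no longer be counted as having hardship, so the proportion affected at one year must be below 30% and 50%. The effect described in words and the effect carried by the hazards are therefore different effects.

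Two things are at stake. Anyone setting observed one-year cumulative incidences by group against the planned 30% vs 50% would use a benchmark that the design hazards do not imply. And the power depends on which effect was meant and on how long each patient is followed, which 7.2 leaves open to a reading that conflicts with 4.7a and 4.9.

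**Working it through.** **Inputs.** From 7.2: hardship hazards 0.356 and 0.693 per year, death hazard m = 0.51, n = 320 (160 per group), two-sided alpha 0.01 (z = 2.576), three years of accrual plus one year. From 7.1: exponential times for both events, and about 10% non-death dropout, censored. From 4.7a and 4.9: at most 12 months per patient. Assumptions added here: hardship and death are independent, the death hazard is the same in both groups, accrual is uniform, and dropout has a constant hazard of -ln(0.90) = 0.105.

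**1. Scale of the printed rates.** 1 - exp(-0.356) = 30.0% and 1 - exp(-0.693) = 50.0%. Also 0.693/0.356 = 1.95 and 1 - exp(-0.51) = 40.0%. The conversions are sound, but 30% and 50% are rates in the absence of death.

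**2. One-year cumulative incidence with death.** CIF(1) = h/(h+m) × [1 - exp(-(h+m))].
- h = 0.356: 0.356/0.866 × (1 - 0.4206) = 23.8%
- h = 0.693: 0.693/1.203 × (1 - 0.3003) = 40.3%
- Difference: 16.5 points.

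**3. Reproducing the stated power.** Read as staggered entry with one to four years of follow-up, the mean cumulative incidence per group, with s = h + m, is h/s × [1 - (exp(-s) - exp(-4s))/(3s)]. This gives 0.349 and 0.529, so 55.9 + 84.7 = 141 events. With ln(0.693/0.356) = 0.666:
- event-variance form: 0.666/√(1/55.9 + 1/84.7) - 2.576 = 1.29, power 90.1%
- Schoenfeld form: 0.666 × √(140.6/4) - 2.576 = 1.37, power 91.5%

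A simulated log-rank test (6,000 replicates) gave 90.7%. At 2:1 the same basis gives 82.9% (event-variance form, larger group at higher risk) or 84.6% (Schoenfeld form, larger group at lower risk), against the stated 83%.

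**4. Same hazards, 12 months per patient.**

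| Setting | Events | Event-variance | Schoenfeld | Simulated |
|---|---|---|---|---|
| 12 months | 38.1 + 64.5 = 102.6 | 75.3% | 78.7% | 77.0% |
| 12 months, 10% dropout | 36.4 + 61.8 = 98.3 | 73.0% | 76.6% | 75.4% |

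At 2:1 and 12 months without dropout, simulated power is 73.8% if the larger group has the lower risk and 67.8% if it has the higher risk.

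**5. Taking 30% and 50% as true cumulative incidences.** Solving CIF(1) = 0.30 and 0.50 with m = 0.51 gives h ≈ 0.471 and 0.951. Check: 0.471/0.981 × (1 - exp(-0.981)) = 0.300, and 0.951/1.461 × (1 - exp(-1.461)) = 0.500. The ratio is 2.02. At 12 months the events are 48 + 80 = 128 and power is 89.9% (event-variance) to 92.0% (Schoenfeld). With 10% dropout there are 123 events and power is 88.4-90.7%.

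**The case against.** The best defence is step 5. If the proportions are the intended effect, a 20-point difference with about 90% power is roughly right at 12 months, and the 2:1 figure (82.0% with a larger higher-risk group, event-variance form; 84.5% with a larger lower-risk group, Schoenfeld form) is also close to 83%. This stands. A reader might infer that the 90% can be recovered only with one to four years of follow-up, or that the study is definitely underpowered. The documents support neither, because they do not say whether the hazards or the proportions define the effect. But this defence requires the printed hazards and the 1.95 to be wrong, so an inconsistency remains either way.

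A second defence is that 30% and 50% are rates among patients alive at one year, which under independence is numerically true and is close to 7.1's basis for its interval, "using an exact binomial in patients with complete follow-up". Section 7.2 makes no such restriction. A third is that the hazards are subdistribution hazards. The text does not say so, and exponential times for both events point to cause-specific hazards. On that reading, 12 months gives 88.3% at 1:1 but 79.5% or 86.9% at 2:1 (Schoenfeld form).

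It is also fair to say that the label alone changes little. The Cox analysis does not depend on it, and no planned test compares group incidences with 30% vs 50%.

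Two further inferences are tempting. One is that 7.1's anticipated 40% must be scaled down in the same way; 7.1 does not say that its 40% is a no-death rate. The other is to attach a range to the 16.5 points for unequal mortality; 7.2 grants that prognosis may be related to the five factors but gives no death rates by group.

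**Conclusion.** The point holds as an inconsistency within 7.2 and between 7.2 and sections 4.7a and 4.9. Under the plan's own inputs, the printed hazards imply 23.8% vs 40.3% at one year (16.5 points, not 20), assuming independence and equal death hazards. With those hazards, 12 months of follow-up gives about 103 events and 75-79% power (73-77% with 10% dropout), not 90%. If 30% vs 50% are instead true cumulative incidences, 12-month power is about 90-92%, but the hazards and hazard ratio are misprinted.

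This is not evidence that the power arithmetic was done wrongly: the stated 90% and 83% do follow from the printed hazards with one to four years per patient. The sentence should be corrected because this objective is said to drive the sample size.

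**What to change.** In 7.2, name the scale of the design effect and the follow-up per patient that the power assumes, and make hazards, proportions and power agree. Two repairs are available, and the sponsor should choose the one that reflects its intent.

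- **(a) Keep the hazards** 0.356 and 0.693 (hazard ratio 1.95). Label 30% vs 50% as rates in the absence of death. Give 23.8% vs 40.3% (16.5 points, assuming equal death hazards) as the one-year cumulative incidences. Restate power at 12 months as about 75-79%, or 73-77% with 10% dropout.
- **(b) Keep 30% vs 50%** as one-year cumulative incidences. Correct the hazards to about 0.471 and 0.951 (hazard ratio about 2.02). Power at 12 months is then about 90-92%, or 88-91% with 10% dropout.

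Under either, recompute the 2:1 power on the same basis and say which group is the larger.

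The cost is a short rewrite of the power paragraph in 7.2. Data collection and the Cox analysis do not change. Under (a) the sponsor must accept or address a lower stated power; under (b) the detectable hazard ratio is slightly larger.
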